6.1.3. Multiple Comparisons

This section details the null hypotheses for this trial. They are presented in the form H_{ij} , where i = trial part ($i = 1, 2$) and j = hypothesis number ($j = 1, 2, 3, 4, 5$).

The hypothesis relates to the primary endpoint of weighted mean IV GIR in the last 12 hours of each treatment period during Part 1. Formally, the hypothesis is:

$$H_{11}: \text{Weighted Mean IV GIR}_{\text{dasiglucagon}} = \text{Weighted Mean IV GIR}_{\text{placebo}}$$

The hypotheses relating to the key secondary endpoint (based on the last 48 hours of each treatment period in Part 1) are:

$$H_{12}: \text{Total amount of carbohydrates administered (regardless of route) per day}_{\text{dasiglucagon}} = \text{total amount of carbohydrates administered (regardless of route) per day}_{\text{placebo}}$$

A fixed-sequence statistical strategy will test the primary and the key secondary endpoint of Part 1 in a predefined order, all at the same significance level ($\alpha = 0.05$, 2-sided test), moving to the next hypothesis only after rejecting the previous null hypothesis.

The test hierarchy is:

Part 1

$$H_{11}: \text{Weighted Mean IV GIR in the last 12 hours of each treatment period during Part 1 (primary endpoint)}$$

$$H_{12}: \text{Total amount of carbohydrates administered (regardless of route) per day (key secondary endpoint)}$$

Inferential analysis will be performed for the secondary endpoint on Weighted Mean GIR during 48-hour period and Mean GIR below 10mg.kg/min in the last 12 hours of each treatment period during Part 1. Results of those analysis are not included in hierarchical testing.

For other secondary endpoints, no inferential statistical analysis is planned, only descriptive.

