with treatment (TRT) and period as fixed effects and patient as a random effect. Denominator degrees of freedom will be calculated according to Kenward Roger method. The 2-sided 95% confidence interval (CI) for the treatment difference will be calculated from the mixed regression model.

Missing data will be imputed as detailed below:

- if the weighted mean IV GIR is missing for the placebo period, it will be imputed using the baseline IV GIR;
- if the weighted mean IV GIR is missing for the dasiglucagon period, it will be imputed using the placebo-weighted mean IV GIR for that patient.

The primary efficacy analysis will be based on the Full Analysis dataset.

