- Sensitivity analysis using a placebo multiple-imputation method will be performed. As for each period of cross-over we have only baseline and end of period value, non-monotone imputation is not needed. Monotone missing values will be imputed using the imputation model built from the placebo group in corresponding period, i.e., assuming the missing data in the Dasiglucagon group will have a profile that equals the profile of the Placebo group. The missing data imputation will be implemented using PROC MI in SAS 9.4 using a monotone regression model approach for each period independantly. The baseline GIR will be included as explanatory variable and the value at the end of the period will be included as the outcome variable in the model. The seed to be used in the analysis is 12255070, and 100 imputed datasets will be created. Once the completed data sets are formed, the same analysis model as specified for the primary analysis will be applied to each completed set and the inference drawn using Rubin's combination rules (SAS proc MIANALYZE).

As a sensitivity analysis, as some subjects did not have the same GIR infusion rate at start of each cross-over period, the same analysis as primary analysis will be run adding as covariate period specific baseline (BASEP) and Mean baseline for subject over the two periods (MEANBASE):

```
PROC MIXED;  
CLASS PATIENT PERIOD TRT;  
MODEL OUTCOME= PERIOD TRT BASEP MEANBASE/ DDFM=KR;  
RANDOM PATIENT;  
LSMEANS TRT / PDIFF CL E;  
RUN;
```

As supportive analysis:

- the primary endpoint analysis will be repeated on the PP Set.
- the primary endpoint will be analyzed using a generalized linear model using a log-link and assuming a normal distribution/ With this analysis, exponentiated estimate for treatment effect would give you the mean(GIR) dasi / mean (GIR) placebo/. Following program will be used:

```
PROC GENMOD;  
CLASS PERIOD TRT;  
MODEL OUTCOME= PERIOD TRT / LINK=LOG DIST=NORMAL ;  
REPEATED SUBJECT=PATIENT/ TYPE=CS;  
ESTIMATE "DASIGLUCAGON versus PLACEBO" TRT 1 -1 / EXP;  
RUN;
```

These sensitivity and supportive analyses will not be included in the fixed-sequence hierarchical testing strategy.

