8.3. Secondary Efficacy Analysis

The secondary efficacy analysis for this study includes the below summaries and inferential analyses. These are continuous endpoints and one binary endpoint and will be summarized using descriptive statistics by study visit (if applicable), treatment group (Part 1) and overall (Part 2) for patients in the FAS. Inference will be performed for Part 1 secondary endpoint as described below. For all the other endpoints no inference will be performed.

Missing data will be imputed for Weighted Mean IV GIR (continuous) as per what is described for primary analysis. The imputed Weighted Mean IV GIR will be used for derivation of Weighted Mean IV GIR below 10 mg/kg/min endpoint. No other imputation for missing data performed and no sensitivity analysis.

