8.3.1. Primary Analyses for Secondary Endpoints

Part 1 (Day 1 to 4, for each 48-hour treatment period)

- Weighted Mean IV GIR for each 48-hour treatment period during Part 1 (dasiglucagon or placebo administration). This endpoint will be analyzed using the same mixed-model regression approach as the one used for primary endpoint and removing IV GIR data that are not valid for site 101. No sensitivity analysis on this endpoint.

- Weighted Mean IV GIR below 10 mg/kg/min in the last 12 hours of each treatment period during Part 1 (yes/no) (dasiglucagon or placebo administration). For this analysis a generalized estimating equation (GEE) method with logit link function will be used using below program and removing IV GIR data that are not valid for site 101.

```
PROC GENMOD;  
  CLASS PATIENT PERIOD TRT;  
  MODEL OUTCOME= PERIOD TRT / LINK=LOGIT DIST=BINOMIAL ;  
  REPEATED SUBJECT=PATIENT/ WITHIN=PERIOD TYPE=CS;  
  LSMEANS TRT / ILINK CL EXP DIFF;  
  ESTIMATE "DASIGLUCAGON versus PLACEBO" TRT 1 -1 ;  
RUN;
```

Part 2 (Day 5 to 25, assessed from the start of treatment in part 2)

If patient needs a pancreatectomy, this will occur only during the Part 2 of the study. If pancreatectomy was done before randomization, it will not be taken into account. Only patients with pancreatectomy during the study will have censored values.

The evaluation of the Part 2 endpoints will then be impacted by pancreatectomy. To be able to assess only treatment effect as primary analysis the following rules will be applied:

- SMPG-detected episode, Carbohydrates administrated, CGM-detected episode, CGM percent time endpoint and extent of hypoglycemia will be set to missing after pancreatectomy (whatever percentage of pancreatectomy).
- Time to complete weaning off IV GIR and time to actual hospital discharge will be censored at time of pancreatectomy (whatever percentage of pancreatectomy).

Following endpoints will be described by week and over the three weeks period.

- Time to complete weaning off IV GIR. Only patient without complete weaning off IV GIR at start of Part 2 will be included in this analysis. Kaplan-Meier estimates will be given for each of the three weeks treatment period.
- Rate of SMPG-detected hypoglycemia episode, defined as number of hypoglycemic events (PG <70 mg/dL or 3.9 mmol/L).
- Rate SMPG-detected Clinically significant hypoglycemia episode, defined as number of events <54 mg/dL (3.0 mmol/L).

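### With 12 patients, the supportive log-link analysis in SAP 8.1.1 has no small-sample correction, so its nominal 95% interval covers about 90-92% under normality; a minor gap in SAP 8.3.1 is that the protocol's McNemar fallback is not carried over

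*SAP*

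**What the plan says.** **Log-link analysis.** Among the supportive analyses in SAP 8.1.1, "the primary endpoint will be analyzed using a generalized linear model using a log-link and assuming a normal distribution". The exponentiated treatment estimate is the ratio of mean GIR on dasiglucagon to mean GIR on placebo. The printed GENMOD program has period and treatment in the model and the statement "REPEATED SUBJECT=PATIENT/ TYPE=CS". It names no small-sample variance, no type of standard error and no degrees of freedom. Its class statement is "CLASS PERIOD TRT", without PATIENT; the GENMOD program in SAP 8.3.1 does list PATIENT.

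**Primary model.** For the mixed model in SAP 8.1, "Denominator degrees of freedom will be calculated according to Kenward Roger method".

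**Responder endpoint** (weighted mean IV GIR below 10 mg/kg/min in the last 12 hours). SAP 8.3.1 says "For this analysis a generalized estimating equation (GEE) method with logit link function will be used using below program", and names no fallback. Section 13.4.3.3 of both protocol versions gives a McNemar test if the GEE does not converge. SAP Section 10 lists no change on this point.

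**Status.** On the log-link analysis: "These sensitivity and supportive analyses will not be included in the fixed-sequence hierarchical testing strategy". On the responder analysis, SAP 6.1.3: "Results of those analysis are not included in hierarchical testing".

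**The concern.** A sandwich variance is biased downwards when there are few clusters, and normal quantiles ignore the uncertainty in that variance. Twelve patients in two sequences of six is well inside the range where both matter. The plan deals with this in the primary model but not in the supportive one. The ratio of means is an easily quoted result, and it would carry a 95% label that it does not earn. A supportive analysis that is too readily significant also gives weaker support than it appears to.

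For the responder endpoint, randomization requires a mean glucose need of at least 10 mg/kg/min over the previous 24 hours (protocol 9.2.3), so responders on placebo may be few. If there are none, the logit treatment effect has no finite estimate. An analyst working from the SAP program alone could then report an unbounded odds ratio.

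**Working it through.** **Inputs.** From SAP 3.2: 12 patients; mean difference 7.5 and SD of differences 7.36 mg/kg/min; GIR 18.5 (12.9, 22.8) before and 11 (6.6, 17.5) after glucagon; differences assumed normal. From SAP 3.5: 1:1 allocation, taken as 6 + 6. From SAP 4.1: two-sided alpha 0.05. SDs are taken as interquartile range / 1.349:
- 9.9 / 1.349 = 7.34 and 10.9 / 1.349 = 8.08.
- Implied within-patient correlation: (7.34² + 8.08² − 7.36²) / (2 × 7.34 × 8.08) = 0.55.

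**Plan's own figure.** One-sample t-test, noncentrality 7.5 / (7.36 / √12) = 3.53, 11 df: power 89.4%. The stated 89% is reproduced.

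**Closed form, identity-link analogue.** With two sequences of six, the sandwich divides by 6 where the unbiased variance divides by 5, so it is 5/6 of the unbiased variance, on 10 df.
- Sandwich with z: P(|t10| < 1.96 × √(5/6)) = P(|t10| < 1.789) = 0.896.
- Mancl-DeRouen with z: P(|t10| < 1.96 × √(6/5)) = P(|t10| < 2.147) = 0.943.
- Sandwich with t on 10 df: P(|t10| < 2.228 × √(5/6)) = P(|t10| < 2.034) = 0.931.

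**Log-link model by simulation** (normal data, 6 + 6 patients, exchangeable correlation, 20,000 runs per scenario):

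| Scenario | Sandwich + z | Mancl-DeRouen + z |
|---|---|---|
| Null, 18.5 / 18.5, SD 7.34 | 89.9% | 94.7% |
| 18.5 / 11, SDs 7.34 / 8.08 | 91.3% | 94.6% |
| 18.5 / 11, five other SD choices or values floored at 0 | 90.1-91.6% | 94.3-95.1% |
| 18.5 / 11, SDs 7.34 / 8.08, floored at 0 | 90.7% | 94.6% |

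A separate set of simulations (8,000 runs each) gave 91.6% at the SAP inputs and 89.8-91.8% in other normal scenarios. In that set the sandwich with t on 10 df gave 94.3% at the SAP inputs. Sandwich-plus-z coverage rose to 93.2% with 24 patients and about 95% with 60, so the shortfall is a small-sample effect.

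**Non-normal data.** With lognormal GIR at the SAP inputs, sandwich plus z covered 86.8% in that set and 87.9% in a further 4,000-run simulation. Mancl-DeRouen plus z gave 91.4% and 91.9%; the sandwich with t on 10 df gave 90.6%.

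**Rejection.** The comparator is a within-patient t-test on 10 df, the complete-data analogue of the primary analysis.
- Null: log-link 10.1%, primary analogue 5.2%. Log-link alone 4.9%, i.e. 4.9 / 10.1 = 49% of its rejections. The 4,000-run simulation gave 9.7% and 5.2%, i.e. 54%. The primary analogue alone: 0.0%.
- Planning effect: log-link 93-94%, Mancl-DeRouen plus z 85-88%, primary analogue 89%. The uncorrected log-link and primary decisions agree in 94-96% of runs.

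**Responder GEE.** The documents give no placebo responder rate, so p is an assumption. P(0 of 12) = (1 − p)^12:
- p = 5%: 0.540
- p = 10%: 0.282
- p = 20%: 0.069
- p = 30%: 0.014

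In a trial fit with no placebo responder, the software reported convergence, with a log odds ratio near 25 and no usable standard error. A trigger worded only as non-convergence may therefore not fire.

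**The case against.** The strongest reply is that neither analysis decides anything. If the primary hypothesis is not rejected, testing stops, and a significant ratio cannot rescue it. At the planning effect the two decisions nearly always agree. This stands, and it limits the weight of the point. It does not make the 95% label right.

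A second reply is that the SAP does not name the type of standard error; the empirical sandwich with normal quantiles is the assumed reading of the program. This is fair, but the model-based error with z covers 90.0% at the SAP inputs, so the shortfall does not depend on that reading.

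Three stronger readings might be inferred, and none is supported:
- *That a false-positive log-link result would nearly always stand alone.* About half of the null rejections are shared with the primary analogue. What holds is the converse: the primary analogue is almost never significant alone.
- *That the SAP withdrew the McNemar rule.* SAP Section 1 names the protocol as reference material and Section 10 withdraws nothing, so the rule can be read as still in force. The gap is mainly one of reconciliation.
- *That the responder GEE is likely to fail.* The probability runs from 54% to 1.4% over the assumed rates. The algorithm in Table 1 also reduces GIR on placebo at every glucose value of 81 mg/dL or more, which could raise the placebo rate. Descriptive summaries by treatment remain planned in SAP 8.3 in any case.

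**Conclusion.** The point holds for the supportive log-link analysis. Its nominal 95% interval covers about 90-92% under normality and about 87-88% with lognormal GIR, and its null rejection rate is about 10% instead of 5%. These figures rest on 12 complete patients split 6 + 6, SDs derived from the quoted quartiles, and sandwich errors with normal quantiles. Neither proposed correction fully restores 95% if GIR is strongly skewed. The missing PATIENT in the CLASS statement is a programming slip; no effect on results is claimed.

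The responder point is minor: an unrepeated fallback, and a trigger that does not name separation. Its probability cannot be fixed from the documents. Primary and key secondary conclusions are unaffected by either point.

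**What to change.** **SAP 8.1.1.** Specify a small-sample method for the log-link model. Either use a Mancl-DeRouen sandwich with normal quantiles, or, more simply, keep the sandwich and refer it to t on 10 df. Add PATIENT to the CLASS statement.

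**SAP 8.3.1.** Keep the GEE and carry over the protocol's McNemar fallback. Define its trigger as non-convergence or a zero or full responder count in either treatment. Say whether the test is exact, and record the wider trigger in Section 10. The case for correction in 8.1.1 does not extend to this GEE: where its estimate is finite, simulated coverage is already 92.6-95.8%.

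**Cost.** A change of code, a sentence in 8.3.1 and a Section 10 entry. The Mancl-DeRouen sandwich may need a SAS procedure other than GENMOD; the t reference avoids a new variance estimator. The Mancl-DeRouen interval is 17-20% wider, and rejection at the planning effect falls from 93-94% to 85-88%. McNemar has no period adjustment. In its exact form, with responders on drug only, p = 2 × 0.5^k for k such patients: five give 0.0625 and six give 0.031.

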8.2. Key Secondary Efficacy Analysis

8.2.1. Primary Analyses for the Key Secondary Endpoint

For the primary analysis of the key secondary endpoint, missing dasiglucagon values during one period will be imputed with the placebo value for that patient, missing placebo values will be imputed with the mean of placebo patients for that period.

Total amount of carbohydrates administered per day

H_{12} : Total amount of carbohydrates administered (regardless of route) per day $_{\text{dasiglucagon}}$ = total amount of carbohydrates administered (regardless of route) per day $_{\text{placebo}}$

This hypothesis will be analyzed by using a mixed-model regression approach, with treatment and period as fixed effects and patient as a random effect. The total amount of carbohydrates administered per day is the sum of the last 48 hours of each period in Part 1 divided by number of days followed.

8.2.2. Sensitivity Analyses for the Key Secondary Endpoints

In addition, a sensitivity analysis will be performed for the key secondary endpoint using complete cases.

8.3. Secondary Efficacy Analysis

The secondary efficacy analysis for this study includes the below summaries and inferential analyses. These are continuous endpoints and one binary endpoint and will be summarized using descriptive statistics by study visit (if applicable), treatment group (Part 1) and overall (Part 2) for patients in the FAS. Inference will be performed for Part 1 secondary endpoint as described below. For all the other endpoints no inference will be performed.

Missing data will be imputed for Weighted Mean IV GIR (continuous) as per what is described for primary analysis. The imputed Weighted Mean IV GIR will be used for derivation of Weighted Mean IV GIR below 10 mg/kg/min endpoint. No other imputation for missing data performed and no sensitivity analysis.

8.3.1. Primary Analyses for Secondary Endpoints

Part 1 (Day 1 to 4, for each 48-hour treatment period)

- Weighted Mean IV GIR for each 48-hour treatment period during Part 1 (dasiglucagon or placebo administration). This endpoint will be analyzed using the same mixed-model regression approach as the one used for primary endpoint and removing IV GIR data that are not valid for site 101. No sensitivity analysis on this endpoint.

- Weighted Mean IV GIR below 10 mg/kg/min in the last 12 hours of each treatment period during Part 1 (yes/no) (dasiglucagon or placebo administration). For this analysis a generalized estimating equation (GEE) method with logit link function will be used using below program and removing IV GIR data that are not valid for site 101.

```
PROC GENMOD;  
  CLASS PATIENT PERIOD TRT;  
  MODEL OUTCOME= PERIOD TRT / LINK=LOGIT DIST=BINOMIAL ;  
  REPEATED SUBJECT=PATIENT/ WITHIN=PERIOD TYPE=CS;  
  LSMEANS TRT / ILINK CL EXP DIFF;  
  ESTIMATE "DASIGLUCAGON versus PLACEBO" TRT 1 -1 ;  
RUN;
```

Part 2 (Day 5 to 25, assessed from the start of treatment in part 2)

If patient needs a pancreatectomy, this will occur only during the Part 2 of the study. If pancreatectomy was done before randomization, it will not be taken into account. Only patients with pancreatectomy during the study will have censored values.

The evaluation of the Part 2 endpoints will then be impacted by pancreatectomy. To be able to assess only treatment effect as primary analysis the following rules will be applied:

- SMPG-detected episode, Carbohydrates administrated, CGM-detected episode, CGM percent time endpoint and extent of hypoglycemia will be set to missing after pancreatectomy (whatever percentage of pancreatectomy).
- Time to complete weaning off IV GIR and time to actual hospital discharge will be censored at time of pancreatectomy (whatever percentage of pancreatectomy).

Following endpoints will be described by week and over the three weeks period.

- Time to complete weaning off IV GIR. Only patient without complete weaning off IV GIR at start of Part 2 will be included in this analysis. Kaplan-Meier estimates will be given for each of the three weeks treatment period.
- Rate of SMPG-detected hypoglycemia episode, defined as number of hypoglycemic events (PG <70 mg/dL or 3.9 mmol/L).
- Rate SMPG-detected Clinically significant hypoglycemia episode, defined as number of events <54 mg/dL (3.0 mmol/L).
- Time to actual hospital discharge. Kaplan-Meier estimates will be given for each of the three weeks treatment period.
- Time to pancreatic surgery (sub-total or total pancreatectomy, cutoff 95% or more).
- Total amount (g) of carbohydrates administered (regardless of route) per day, together with amounts (g) of carbohydrates administered per day:
 - via IV glucose infusion or bolus (not as part of total parenteral nutrition),
 - as part of total parenteral nutrition (if applicable),
 - via oral route, and
 - via NG tube or gastrostomy.
- CGM percent time in range 70-180 mg/dL (3.9-10.0 mmol/L).

- CGM percent time in hypoglycemia (<70 mg/dL or 3.9 mmol/L).
- CGM percent time in clinically significant hypoglycemia (<54 mg/dL or 3.0 mmol/L).
- Rate of CGM-detected hypoglycemia episodes, defined as number of episodes <70 mg/dL (3.9 mmol/L) for 15 min or more.
- Rate of CGM-detected clinically significant hypoglycemia episodes, defined as number of episodes <54 mg/dL (3.0 mmol/L) for 15 min or more.
- Extent of hypoglycemia (area over the glucose curve [AOC_{glucose}] below 70 mg/dL [3.9 mmol/L]) as measured by CGM. Extent of hypoglycemia will be presented in mmol/L and mg/dL.
- Extent of clinically significant hypoglycemia (AOC_{glucose} below 54 mg/dL [3.0 mmol/L]) as measured by CGM. Extent of hypoglycemia will be presented in mmol/L and mg/dL.
- CGM percent time in hyperglycemia (>180 mg/dL or 10.0 mmol/L).

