4.1. Introduction

Data processing, tabulation of descriptive statistics, calculation of inferential statistics, and graphical representations will be performed primarily using SAS (release 9.4 or higher). If the use of other software is warranted, the final statistical methodology report will detail what software was used for what purposes.

Continuous (quantitative) variable summaries will include the number of subjects (n) with non-missing values, mean, standard deviation (SD), median, minimum, and maximum.

Categorical (qualitative) variable summaries will include the frequency and percentage of subjects who are in the particular category or each possible value. In general, the denominator for the percentage calculation will be based upon the total number of subjects in the study population for the within each treatment group, unless otherwise specified. The denominator for by-visit displays will be the number of patients in the relevant study population with non-missing data at each visit.

The minimum and maximum will be reported with the same degree of precision (ie, the same number of decimal places) as the observed data. Measures of location (mean and median) will be reported to 1 degree of precision more than the observed data and measures of spread (SD) will be reported to 2 degrees of precision more than the observed data.

Percentages will be presented to 1 decimal place, unless otherwise specified.

Unless otherwise indicated, all testing of statistical significance will be 2-sided with a significance level of $\alpha = 0.05$.

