- **Weighted Mean IV GIR threshold:** This variable will be assigned “Yes” when the Weighted Mean IV GIR calculated over 12 hours period is not missing and < 10mg/kg/min and will be assigned “No” when value calculated will be $\geq 10\text{mg/kg/min}$.
- **Z-scores:** For subjects who are less than 2 years of age, WHO growth charts will be used to calculate Z-scores, as described here: 'www.cdc.gov/nccdphp/dnpao/growthcharts/resources/sas-who.htm'. For subjects who are greater than or equal to 2 years of age, Z-scores will be derived based on the SAS program in link 'www.cdc.gov/nccdphp/dnpao/growthcharts/resources/sas.htm' by using SEXN, Age in months ((VSDAT-ADSL.BRTHDT)/30.4375) and corresponding weight/height at baseline measurements.

- **PK Clearance:**

$$CL/f \text{ (L/h)} = R_0/C_{ss}$$

where R_0 = infusion rate (pmol/h) and C_{ss} = concentration at steady state (pmol/L), weight
($1\mu\text{g}/\text{kg}/\text{hr} = 295.7 \text{ nmol}/\text{kg}/\text{h}$)

- **Primary endpoint IV GIR:** Values from SDTM.EX where EXTRT="IV GLUCOSE INFUSION", not including the "IV GLUCOSE BOLUS".
- **Total amount of carbohydrates received:**

Calculated as the sum of carbohydrates received via IV glucose infusion or bolus, as part of total parenteral nutrition, via oral route and via NG tube or gastrostomy. This average daily value will be used in analysis calculated as the sum of carbohydrates received divided by number of days in corresponding period. As IV glucose infusion is recorded in mg/kg/min, for each analysis period, the total amount received will be calculated as:

$$\text{IV glucose infusion (mg)} = \text{Infusion rate recorded in CRF} \times \text{WGT} \times \text{TIME}$$

with WGT = weight at beginning of the analysis period, TIME = duration of analysis period in minutes

IV glucose infusion or bolus are reported in SDTM.EX with EXTRT in "IV GLUCOSE INFUSION" or "IV GLUCOSE BOLUS".

Carbohydrates received via oral route, via NG tube or gastrostomy are reported under Carbohydrates administration eCRF.

Total parenteral nutrition is reported under Carbohydrates administration eCRF selecting observations specified as part of TPN.

- **Nightly gastric carbohydrates to treat hypoglycemia** = amount of gastric carbohydrates (g) given between midnight and 6 am inclusive to treat hypoglycemia.

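### The SAP program for the under-10 mg/kg/min responder endpoint names no event level; with Yes/No or 0/1 coding and software defaults it estimates non-response (minor)

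*SAP*

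**What the plan says.** SAP 6.1.7 (Weighted Mean IV GIR threshold) defines the variable in words: "This variable will be assigned “Yes” when the Weighted Mean IV GIR calculated over 12 hours period is not missing" and is under 10 mg/kg/min; it "will be assigned “No” when value calculated will be" 10 mg/kg/min or more. The response of interest is therefore Yes.

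SAP 8.3.1 states that the analysis is a GEE with a logit link and refers to a printed program. Its relevant lines are:

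- "MODEL OUTCOME= PERIOD TRT / LINK=LOGIT DIST=BINOMIAL", with no `EVENT=` or `REF=` option after `OUTCOME` and no `DESCENDING` option on the procedure line;
- "LSMEANS TRT / ILINK CL EXP DIFF", which asks for back-transformed probabilities and exponentiated differences;
- "ESTIMATE 'DASIGLUCAGON versus PLACEBO' TRT 1 -1", without `EXP`, so on the log-odds scale only.

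SAP 4.1 says that the analyses "will be performed primarily using SAS (release 9.4 or higher"). Protocol 13.4.3.3 specifies a GEE with a logit link, and a McNemar test if it does not converge, but gives no modelled level. SAP 6.1.3 makes this one of two secondary endpoints outside the hierarchy that still receive inferential analysis.

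**The concern.** A logistic model for a binary variable estimates the odds of one of its two levels. If the program does not say which, the software's ordering rule decides. The SAP's own labels put No ahead of Yes, so the printed program would model the chance of not getting under 10 mg/kg/min, although the endpoint is defined as getting under it.

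At stake is the direction of one reported estimate. A favourable effect of dasiglucagon would appear as an odds ratio below 1. The model-based proportions under a responder heading would be non-responder proportions.

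**Working it through.** **Inputs**

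- Coding Yes (<10) or No (≥10): SAP 6.1.7.
- Program statements and their options: SAP 8.3.1.
- Software, SAS 9.4 or later: SAP 4.1.
- Sample size, 12 patients: SAP 3.2.
- Assumption from general software knowledge, not in the documents: PROC GENMOD sorts the response levels and models the lowest.
- Assumption: responder counts. The documents give no expected rates, so a range is used.

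**Plan's own figure.** None is stated for this endpoint. The only power figure is for the primary endpoint. It reproduces (difference 7.5, SD 7.36, n = 12, two-sided one-sample t-test, df = 11: 89.4% against the stated 89%) but has no bearing here.

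**Step 1: which level is modelled.** Sorted, the levels are No, Yes. The modelled probability is P(No). With 0/1 coding and 1 = Yes, the lowest level is 0, again non-response.

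**Step 2: direction of the contrast.** If treatment is held by name, Dasiglucagon sorts before Placebo. `TRT 1 -1` is then dasiglucagon minus placebo, as its label says, and nothing offsets step 1.

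**Step 3: effect on the output.** Since logit P(No) = −logit P(Yes):

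- `ILINK` returns 1 − P(Yes);
- `EXP DIFF` on LSMEANS returns 1/OR;
- `ESTIMATE` returns −log OR;
- the test statistic changes sign only, so the two-sided p-value is the same, and the confidence limits for the odds ratio are inverted and swapped.

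**Step 4: size.** A logit GEE (period and treatment, patient clusters, exchangeable correlation to match `TYPE=CS`) was fitted outside SAS to assumed data on 12 patients, six per sequence. Each data set was fitted once for Yes and once for No. The patient pattern is given as responders on both treatments / dasiglucagon only / placebo only / neither.

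| Responders, dasiglucagon vs placebo | Pattern | Crude OR for Yes | GEE OR for Yes (95% CI) | GEE OR for No (95% CI) | p, both fits |
|---|---|---|---|---|---|
| 6/12 vs 4/12 | 3/3/1/5 | (6/6)/(4/8) = 2.0 | 2.08 (0.575–7.50) | 0.48 (0.133–1.74) | 0.26 |
| 8/12 vs 3/12 | 2/6/1/3 | (8/4)/(3/9) = 6.0 | 6.11 (1.08–34.5) | 0.164 (0.029–0.924) | 0.040 |
| 9/12 vs 2/12 | 1/8/1/2 | (9/3)/(2/10) = 15 | 15.7 (1.78–138) | 0.064 (0.007–0.562) | 0.013 |

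In each row the two odds ratios are reciprocals: 1/2.0772 = 0.481, 1/6.1082 = 0.164, 1/15.6847 = 0.064. In the middle row, crude response of 67% vs 25% corresponds to non-response of 4/12 = 33% vs 9/12 = 75%.

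**The case against.** The best reply is that the printed code is a skeleton. `OUTCOME` is a placeholder, used also for the continuous GIR in SAP 8.1, and no dataset, format or ordering option is given. The stored coding is therefore unknown. If it were 1 = Yes and 2 = No, Yes would sort first and nothing would reverse. If placebo sorted first in `TRT`, the second reversal would restore the sign of the contrast, though the `ESTIMATE` label would then be wrong and the `ILINK` proportions would still be for non-response. The ordering default is also software behaviour, not document text. This stands: the reversal is conditional. What remains is that the only coding the SAP states leads to it, and that the program leaves the event level unnamed whatever the default.

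A reader might go further and infer that the report will show benefit as harm. The documents do not support that. SAP 8.3 requires descriptive summaries by treatment group for Part 1, and SAP 4.1 requires counts and percentages for categorical variables. Observed responder rates would therefore sit beside model proportions that contradict them. The prose definition of the endpoint is also clear, so the intended direction is not in doubt.

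A reader might also take the inverted odds ratio to come from the line labelled dasiglucagon versus placebo. It does not: that line has no `EXP`, and the exponentiated contrast comes from LSMEANS.

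**Conclusion.** The point holds in conditional form and is minor. SAP 8.3.1 does not name the modelled level. Given Yes/No coding as in SAP 6.1.7 (or 0/1 with 1 = Yes), treatment levels ordered with dasiglucagon first, and the usual PROC GENMOD default, the program as printed estimates the odds of not being under 10 mg/kg/min. The reported odds ratio is then exactly the reciprocal of the intended one, whatever the true responder rates; the counts used here only illustrate the range.

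It should not be read as a threat to the trial's inference. Significance is the same either way, the endpoint lies outside the fixed sequence (SAP 6.1.3), and the primary and key secondary analyses use different programs. What is affected is the direction of one secondary estimate and the meaning of its model-based proportions.

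**What to change.** In SAP 8.3.1, write `MODEL OUTCOME(EVENT='Yes') = PERIOD TRT`, keeping the existing link and distribution options. Add one sentence stating the order of the `TRT` levels, so that `TRT 1 -1` is dasiglucagon minus placebo. Adding `EXP` to the `ESTIMATE` statement is optional: it would match the log-link program in SAP 8.1.1 but largely repeats what LSMEANS already gives.

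The cost is one option and one sentence. Nothing changes in conduct, data collection, sample size or any other analysis.
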